## 2.2.2. Secondary Outcomes

Secondary outcome measures include 1) Accelerometry data captured using the wearable biosensors and compared to observations of infant position made by a study team member during KC sessions to validate the accuracy of these biosensors in detecting body position and movement during KC; 2) Infant salivary cortisol reactivity, maternal salivary cortisol reactivity, and paternal salivary cortisol, testosterone, and oxytocin reactivity, compared before, during, and after KC; 3) Parenting confidence, relationship quality, and involvement scores as quantitated by the Parenting Sense of Competence Scale (PSOC), the Revised Dyadic Adjustment Scale (RDAS), the Postpartum Bonding Questionnaire, and a Father Involvement Scale at baseline, before discharge, two weeks after discharge, and four weeks after discharge. Two-sample t tests and mixed-effect linear regression models will be used to assess the mean between-group differences. Covariates such as age, education, socio-economic status (SES), stress and depression will be adjusted in the multivariable regression model.

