# 2. Study Hypothesis and Outcomes

# 2.1. Study Hypothesis

The main hypothesis of this study is that Kangaroo Father Care (KFC) will positively impact acute physiologic and long-term behavioral outcomes in infants, fathers, and families.

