# 3. Study Design

# 3.1. Eligibility Criteria

# 3.1.1. Inclusion Criteria

Infants: Infants who are born at Prentice Women's Hospital between 30 0/7 and 36 6/7 weeks gestation, are ≤20 days old at the time of enrollment, and do not meet any of the study's exclusion criteria will be eligible for participation in this study. Additionally, infants will only be included in this study if both of their biological parents are eligible and agree to participate.

Parents: Parents who are  $\geq$ 18 years of age, English speaking, expect mother and father to raise the infant together in the same household regardless of their marital status, and do not meet any of the study's exclusion criteria will be eligible for participation in this study. Additionally, family units will only be included in this study if both biological parents of the infant are eligible and agree to participate.

Only English speaking parents will be included in this trial because the study questionnaires are only available in English.

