#### Kangaroo Care (KC) Intervention:

After enrollment, families will be scheduled to participate in two sessions of KC. The goal will be to schedule the KC sessions over two sequential days and at approximately the same time of day (i.e. morning, afternoon, or evening). However, if this is not possible given the parents' schedules, the sessions will be scheduled for the days and time of day that participating parents are able to visit their infant in the NICU. Each session will include two hours of continuous KC, with one day focused on Kangaroo Mother Care (KMC) and the other on Kangaroo Father Care (KFC), in a randomized order. These sessions will include continuous skin-to-skin holding of the infant by the parent, per standard of care protocol.

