#### **Psychosocial Questionnaires:**

This study will employ psychosocial measures to capture the short- and long-term impacts of KFC. Specifically, validated measures of parenting confidence, relationship quality, infant bonding, and father involvement will be assessed via a set of paper or REDCap surveys administered in the NICU (short term) at baseline and the day before discharge (T-1), and at home (long term) at 2 weeks (T+14) and 4 weeks (T+30) after discharge. Each of these sets of surveys will take approximately 30 minutes to complete. At baseline, each parent will complete the Revised Dyadic Adjustment Scale (RDAS) and the Postpartum Bonding Questionnaire (PBQ). At T-1, each parent will complete the RDAS , the PBQ, and the Parenting Sense of Competence Scale (PSOC). These questionnaires will be completed on paper or directly in REDCap, depending upon the participant's preferences. Data provided on surveys completed on paper will be transferred to secure REDCap forms by study staff and destroyed within 24 hours. At T+14 and T+30, each parent will complete the RDAS, the PBQ, the PSOC, and a Father Involvement Questionnaire. These questionnaires will be completed directly in REDCap only. Each parent will complete the RDAS, the PBQ, the PSOC, and a Father Involvement

receive an email containing a link to their set of questionnaires at both post-discharge time points. All questionnaire data will be stored long term on the secure REDCap server housed by Northwestern University.

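### Section 2.2.2 plans two-sample t tests between unnamed groups; randomisation creates only two session orders, and no controlled contrast isolates a long-term KFC effect on the questionnaires

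*Combined protocol and SAP*

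**What the plan says.** The main hypothesis in Section 2.1 is that "Kangaroo Father Care (KFC) will positively impact acute physiologic and long-term behavioral outcomes in infants, fathers, and families". Section 3.3 (Psychosocial Questionnaires) gives the scales the task of testing the long-term part: "This study will employ psychosocial measures to capture the short- and long-term impacts of KFC".

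Section 2.2.2 lists three secondary outcomes: accelerometry, saliva markers and questionnaire scores. It then closes with the analysis: "Two-sample t tests and mixed-effect linear regression models will be used to assess the mean between-group differences". The next sentence adds: "Covariates such as age, education, socio-economic status (SES), stress and depression will be adjusted in the multivariable regression model". Neither sentence says what the groups are.

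On design, Section 3.1.1 requires couples: "family units will only be included in this study if both biological parents of the infant are eligible and agree to participate". Section 3.3 (Kangaroo Care Intervention) schedules two sessions for every family, "with one day focused on Kangaroo Mother Care (KMC) and the other on Kangaroo Father Care (KFC), in a randomized order". There is no arm without KFC.

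Section 5.1 assigns repeated-measures ANOVA over study phase to the saliva markers, multilevel models to sensor agreement, and within-triad correlations to the hormones. It gives the questionnaires no analysis.

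**The concern.** A two-sample t test needs two independent groups. This design supplies one such pair by randomisation, the two session orders, and that comparison does not measure what KFC does. The other contrasts an analyst might choose are mother versus father, KFC versus KMC, and after versus before. All of these are within family or within person, and for the questionnaires none has a control that separates KFC from everything else that happens to the family.

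Two things are at stake. First, the contrast is left to the analyst, possibly after the data are seen, although the stated aim is a long-term KFC effect that the questionnaires cannot isolate. Second, if a within-family contrast is chosen, the named t test misstates its error. The mixed model, also named, could carry the dependence, but no random effects or covariance are given.

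**Working it through.** **The plan's own figure.** Section 5.1 claims power above 99% for all planned analyses. It cannot be reproduced, because no number of families, effect size, SD, intraclass correlation or dropout is stated. As a scale only, suppose the groups were the two orders, split equally, with N families in total. Power is then about Φ(d·√(N/4) − 1.96). For an assumed d = 0.5 this gives 12%, 20%, 28%, 42% and 71% at N = 10, 20, 30, 50 and 100. Reaching 99% takes 2(1.96 + 2.326)²/0.5² ≈ 147 families per order. Even that would be power for an order effect.

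**Which outcomes the sentence governs.** It follows all three secondary outcomes. The listed covariates fit the questionnaires best, and Section 5.1 leaves only the questionnaires and accelerometry without a group or phase analysis. It may still cover the saliva outcomes.

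**Session order.** Write a family's follow-up mean as μ + KFC effect + KMC effect, plus an order term if KFC came first. Subtracting one order from the other leaves only the order term. A simulation check used 20 + 20 families (assumed), one score per family and 200,000 trials. With a common KFC shift of 0, 0.5 or 1.0 SD, the test rejects in 4.9%, 5.0% and 4.9% of trials. The test is valid, but it carries no information on a common KFC effect.

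**Mother versus father.** Take N couples, equal SD σ and within-couple correlation ρ (assumed). The variance of the mean difference is 2σ²(1 − ρ)/N, whereas the two-sample test uses 2σ²/N. The large-sample true size of a nominal 5% test is 2[1 − Φ(1.96/√(1 − ρ))]. If session order were tested with both parents entered as separate independent rows, 1 + ρ would replace 1 − ρ.

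| ρ (assumed) | mother-father, unpaired | order, both parents as separate rows |
|---|---|---|
| -0.2 | 7.4% | 2.8% |
| 0.3 | 1.9% | 8.6% |
| 0.5 | 0.6% | 11.0% |
| 0.7 | 0.03% | 13.3% |

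Power for a 0.5 SD mother-father difference at ρ = 0.5, unpaired against paired: 29% and 56% with 20 couples, 47% and 75% with 30, 64% and 87% with 40, 85% and 97% with 60. Whatever the test, this contrast is confounded with parental role.

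**KFC versus KMC on the questionnaires.** The scales are scheduled at baseline, the day before discharge, and two and four weeks after discharge. No survey is placed between the two sessions, so this contrast cannot be formed.

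**Change from baseline (RDAS, PBQ).** This change is uncontrolled. It mixes KFC with KMC, time and discharge. Suppose KFC does nothing, time or discharge shifts scores by 0.3 SD, and the before-after correlation is 0.5 (all assumed). The SD of the change is √(2(1 − 0.5)) = 1, and the noncentrality is 0.3√n. A paired t test is then significant in 25%, 46% and 63% of trials with 20, 40 and 60 fathers.

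**PSOC and Father Involvement.** Section 2.2.2 lists all the scales at baseline. Section 3.3 lists only RDAS and PBQ there, adds PSOC the day before discharge, and brings in Father Involvement after discharge: "At T+14 and T+30, each parent will complete the RDAS, the PBQ, the PSOC, and a Father Involvement Questionnaire". If Section 3.3 is followed, these two scales have no change from baseline either.

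**The case against.** The strongest reply is that the plan has not chosen a wrong test; it has left the contrast open. A session-order test with one score per family is valid at 5%. The mixed model can handle correlated parents. The outcomes are secondary. All of this stands, and it limits the point in several ways.

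- A reader might infer that the t test will produce false positives. The documents do not support that. They give no correlation, and if it is positive the unpaired mother-father test is conservative, so the cost is lost power. Inflation needs a negative correlation, or both parents entered as independent rows in an order test, which no section proposes.
- A reader might infer that a particular covariance, such as unstructured, is required. That rests on assuming a negative correlation. In simulation a family random intercept keeps the mother-father size at 5.0-5.3% for correlations of 0.2 and 0.5, and it rises to about 7% only at -0.2.
- A reader might infer that the acute KFC-versus-KMC comparison is untouched, or that it too is lost. Neither is supported. The design allows that comparison within infant, but Section 5.1 writes no such test. If the Section 2.2.2 sentence covers saliva, the comparison would need a within-family analysis as well.
- A reader might infer that an order or before-after result will be presented as a KFC effect. No passage says so; the wording only leaves room for it.

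What does not fall away is the missing comparator. No model or covariate set supplies one when every family receives KFC.

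**Conclusion.** The point holds and should be fixed. Two parts rest on the text and the design alone: the groups are unnamed, and no controlled contrast isolates the long-term KFC effect on the questionnaires. The third part is conditional: a two-sample t test gives the wrong standard error if the contrast chosen is within family, and the sign of the within-family correlation decides whether that costs power or inflates error. Every numerical illustration uses assumed N, correlation and effect size, and the conclusion does not depend on them. The point concerns the secondary outcomes and the long-term part of the main hypothesis. It does not show that the trial cannot study acute KFC effects. The absence of baseline PSOC and Father Involvement scores is not certain either, because Sections 2.2.2 and 3.3 disagree.

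**What to change.** In Sections 2.2.2 and 5.1:

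- Name the contrast for each questionnaire scale and say whether the sentence also governs the saliva outcomes.
- For every within-family contrast, replace the two-sample t test with a paired test or the mixed model already named. The model should account for family and for repeated scores within person, and include session order.
- Keep a two-sample test only for session order, with one score per family, labelled as an order effect.
- State that the questionnaire results describe change over time, mother-father differences and order, and do not estimate a KFC effect. Narrow the long-term part of Sections 2.1 and 3.3 to match.
- Adjust only for covariates actually collected. Section 2.2.2 names stress and depression, but Section 3.3 names no instrument for either and does not describe the content of the saliva questionnaire.
- Reconcile Sections 2.2.2 and 3.3 on which scales are taken at baseline.
- For Father Involvement, which both parents complete, say what a mother-father difference would mean; the documents do not describe the scale.

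The cost is wording in Sections 2.1, 2.2.2 and 3.3 and a short questionnaire paragraph in Section 5.1. Whether any further data are needed depends on the covariate and baseline points. The downside is a more modest long-term claim.

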# 5. Statistical Analysis

## 5.1. Statistical Plan

Measurements made through clinical standard of care will be compared to the measurements recorded by the wearable sensors. Distribution checks for normality and data accuracy will be completed for each individual and for the entire study prior to all analyses. For continuous measures of physiology, 30 second epochs will be defined for each method for comparison.

Agreement and correlation of wearable biosensor measures to standard of care measures will be assessed in two ways. First, Bland–Altman plots will be created to assess agreement between each measurement system via bias and precision, which reflect the mean or average difference between two methods and the variation in these differences, respectively. Our second method consists of individual correlations between methods assessed for each person. This correlational method will supplement additional methods, and can be directly transformed to variance shared between wearable biosensor and standard of care measures, a common metric of reliability of any measure.

Formal tests of bias, precision, and correlations: While the above methods will yield useful statistics, they need to be extended to deal with the structured nature of our data. Specifically, our data are clustered, meaning that we have multiple observations within each person and multiple people in our sample, which violates standard independence assumptions inherent to many models. We propose to estimate bias and correlation/reliability using multi-level models, which yield the same statistics discussed above but account for the fact that observations taken from the same patient are more related than comparisons involving different patients.

Data will be cleaned and analyzed using IBM SPSS Statistics 20.0, unless a newer version of SPSS is available. Using repeated-measures analysis of variance (RM-ANOVA), with the study phase (pre-, during-, and post-kangaroo care) as the repeated factor, we will test differences across study phase for maternal cortisol, paternal cortisol, infant cortisol, paternal oxytocin, and paternal testosterone. We will use a two-tailed test with a 5% level of significance analysis. In addition to tracking changes over the period of kangaroo care, we will also examine within-triad correlations in cortisol for mother-father-

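### For RDAS and PBQ, the plan does not say how the baseline score enters the between-group analysis, and using it would add precision to the randomised order comparison at little cost

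*Combined protocol and SAP*

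**What the plan says.** Section 2.2.2 (Secondary Outcomes) gives the only analysis of the questionnaire scores: "Two-sample t tests and mixed-effect linear regression models will be used to assess the mean between-group differences". The next sentence sets the adjustment: "Covariates such as age, education, socio-economic status (SES), stress and depression will be adjusted in the multivariable regression model". The same section lists the assessment times for all the scales together as "at baseline, before discharge, two weeks after discharge, and four weeks after discharge".

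Section 3.3 (Psychosocial Questionnaires) gives a schedule that differs by scale. RDAS and PBQ start at baseline: "At baseline, each parent will complete the Revised Dyadic Adjustment Scale (RDAS) and the Postpartum Bonding Questionnaire (PBQ". PSOC is added on the day before discharge (T-1). The Father Involvement Questionnaire appears only after discharge: "At T+14 and T+30, each parent will complete the RDAS, the PBQ, the PSOC, and a Father Involvement Questionnaire".

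Section 3.3 (Kangaroo Care Intervention) has every family do two sessions, "with one day focused on Kangaroo Mother Care (KMC) and the other on Kangaroo Father Care (KFC), in a randomized order". Section 5.1 contains no model for the questionnaires.

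**The concern.** A parent's earlier score on a scale is usually one of the best predictors of the later score on that scale. If baseline RDAS or PBQ is left out of a comparison of randomised groups, differences between parents that existed before any study KC stay in the error term, and chance baseline imbalance stays in the estimate. The data to remove both are already being collected from each parent.

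The plan does not say whether they will be used. It does not say whether the t tests are on raw or change scores, whether baseline is a covariate or a response in the mixed model, or which groups are compared. These choices differ in precision, and leaving them open allows them to be made after the data are seen. Long-term behavioural outcomes in fathers and families are part of the main hypothesis in section 2.1, so the questionnaire analysis matters to the trial's stated aim.

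**Working it through.** **The plan's own figure.** Section 5.1 claims power above 99% for nested designs. It cannot be reproduced: no number of families, effect size, SD or correlation is given. It rests on the volume of within-person data, which does not describe questionnaires completed at most four times per parent.

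**Which scales have a baseline (section 3.3)**

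| Scale | Baseline | T-1 | T+14 | T+30 |
|---|---|---|---|---|
| RDAS | yes | yes | yes | yes |
| PBQ | yes | yes | yes | yes |
| PSOC | no | yes | yes | yes |
| Father Involvement | no | no | yes | yes |

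The point is therefore limited to RDAS and PBQ.

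**Variance of a randomised group difference at one follow-up**, relative to an unadjusted raw-score comparison, with r the baseline to follow-up correlation (assumed) and equal SDs at the two times:
- baseline as covariate: 1 − r²
- change from baseline: 2(1 − r)

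| r (assumed) | Raw score | Change score | Baseline as covariate | Cut from covariate |
|---|---|---|---|---|
| 0.3 | 1.00 | 1.40 | 0.91 | 9% |
| 0.5 | 1.00 | 1.00 | 0.75 | 25% |
| 0.6 | 1.00 | 0.80 | 0.64 | 36% |
| 0.7 | 1.00 | 0.60 | 0.51 | 49% |

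A mixed model that takes baseline as a response, leaves all group-by-time means free and contrasts change from baseline has the change-score variance. If the baseline means are constrained equal across groups, it matches the covariate analysis.

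**Power illustration.** Assumptions: n = 20 families per order group, one parent per family, a difference of 0.7 SD at one follow-up, and two-sided 5%. Section 5.1 states that level in its paragraph on the hormone analyses; it is assumed to apply here. Noncentral t with noncentrality 0.7 / √(v × 2/20), where v is the relative variance above. Degrees of freedom are 2n − 2 = 38, or 37 with the covariate.
- Raw score: 0.7 / √0.1 = 2.214, power 57.8%.
- Covariate, r = 0.3: 0.7 / √(0.91 × 0.1) = 2.320, power 61.8%.
- Covariate, r = 0.5: 2.556, power 70.2%.
- Covariate, r = 0.6: 2.767, power 76.9%.
- Covariate, r = 0.7: 3.100, power 85.5%.
- Change-score t test at r = 0.3, 0.5, 0.6, 0.7: 44.6%, 57.8%, 67.4%, 79.5%.

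Allowing for chance imbalance in the covariate lowers the adjusted figures by about one point.

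**Sensitivity.** At 10 per group, 0.8 SD and r = 0.3, with that allowance, power moves only from 39.5% to 40.4%. At 20 per group and 0.2 SD, it moves from 9% to between 10% and 14% over r = 0.3 to 0.7.

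**The case against.** A reader might infer that the plan has decided against baseline adjustment and so discards a known amount of power. The documents do not support that, for these reasons:

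- The covariate list opens with words that make it illustrative, and baseline is one of the listed outcome times, so the mixed model may already use it as a response. What can be shown is that its handling is unspecified.
- A two-sample t test on change scores does use baseline. At r = 0.7 such a test has 79.5% power against 85.5% for the covariate model. The gap is then 6 points, against about 28 points when the comparator is a raw-score test.
- The planned regression already adjusts for stress and depression, which plausibly share variance with relationship and bonding scores. The gain over that model would be smaller than 1 − r² implies.
- The groups are undefined. In the order contrast both arms have had the same two sessions by the later assessments, so it does not estimate a KFC effect, and nothing in the documents supports an order effect of 0.7 SD. If mothers are compared with fathers, the groups are not randomised and are paired within family. Baseline adjustment then changes what is estimated, and a two-sample t test ignores the pairing.

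All of this stands and limits the claim. It does not remove it. An open list leaves the covariate to be chosen later. A free change-from-baseline contrast is less precise than ignoring baseline when r is below 0.5. In every case computed for the order contrast, the covariate model had more power than both the raw-score and the change-score t test.

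**Conclusion.** The point holds in a limited form. For RDAS and PBQ, baseline is collected from both parents but the plan does not say how it enters the analysis; for the randomised order contrast, a model adjusted for it is better than the named t tests. Over assumed r = 0.3 to 0.7 the variance falls by 9% to 49% relative to an unadjusted raw-score comparison at one follow-up, and by less relative to a regression already adjusted for stress and depression. Power at an assumed 20 per group and 0.7 SD rises from 58% to between 62% and 86%. Sample size, effect and correlation are all assumptions; at low r or small n the gain is slight.

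The precision argument does not extend to PSOC or Father Involvement, which have no baseline in section 3.3, and it does not carry over to a comparison of mothers with fathers. Sections 2.2.2 and 3.3 disagree on which scales have a baseline and must be reconciled.

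**What to change.** In section 2.2.2:

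1. Define the groups compared. The only randomised contrast is KMC-first versus KFC-first.
2. For that contrast, make the analysis of record for RDAS and PBQ at T-1, T+14 and T+30 a mixed model with the same parent's baseline score as a covariate, or with baseline as a response and group means at baseline constrained equal. Report the two-sample t tests as descriptive only.
3. If mothers are to be compared with fathers, specify separately an analysis that reflects the pairing within family.
4. Reconcile the assessment times with section 3.3, so that PSOC and Father Involvement are not listed with a baseline they do not have.

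In section 3.3, state that the baseline questionnaires are completed before the first study KC session; the text does not now tie baseline to that point.

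The cost is a few sentences in section 2.2.2 and one procedural sentence in section 3.3. No new questionnaire is needed for RDAS or PBQ, but staff must keep to the timing.

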In contrast to KMC, conspicuously little research has been published about the implementation and benefits of Kangaroo Father Care (KFC). The limited preliminary data that are available support an association between KFC and improved preterm infant physiologic stability (e.g. heart rate variability, respiratory status, blood glucose, oxygen saturation (13)), infant contentment (e.g. crying episodes (12), time to relaxed state (13) and father-infant bonding (12). While both mothers and fathers have been noted to experience doubt, stress, anxiety, depression and loss of control (16) in the NICU, fathers are faced with different challenges than mothers (17,18). Specifically, fathers have been shown to feel less important and less needed than mothers (19), un-empowered in terms of active participation at the bedside, and relegated to return to work and handle external affairs (20). Fathers also report a lack of confidence in how to interact with and care for their premature infant, including a fear of caring for the infant based on the infant's size and perceived fragility (17). Research suggests that these feelings can interrupt the father-infant bond (21). Additionally, fathers have been shown to hide their feelings and return to work while their infant is still in the NICU (19, 22-24) and to experience "pervasive uncertainty" when transitioning home (18). These feelings and experiences may further translate into individual and interpersonal stress, anxiety, and diminished parenting confidence. KFC may be an effective mechanism to support fathers through these experiences, so they can, in turn, better support infants and mothers.

Even though the short and long-term benefits, including cost-effectiveness, of KMC are clear and the World Health Organization recommends that KC be utilized as continuously as possible during the neonatal period (9), the benefits of KFC are only emerging and KC remains thoroughly under-utilized (14) in the NICU (15). We propose to revolutionize KC in the NICU by objectively measuring the effects of the KFC intervention on infants, fathers, and families. Utilizing wireless biosensor technology designed

by members of this team, our study will be the first of its kind to objectively evaluate KFC as an intervention for improving both acute and long-term outcomes of infants, mothers, and fathers in the NICU.

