# 2.2. Outcome Measures

## 2.2.1. Primary Outcome

Primary outcome measures include heart rate (HR) and oxygen saturation (SpO2) as indicators of cardiorespiratory stability in infants before, during, and after KC and HR and HR variability (HRV) as indicators of physiologic stress in NICU parents during and after periods of KC. All of these outcomes will be measured using wearable, wireless biosensors.

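### The questionnaire model adjusts for stress and depression, but no scale for either is scheduled and no time point is given, so values taken after kangaroo care begins could enter the model

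*Combined protocol and SAP*

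**What the plan says.** Section 2.2.2 sets the analysis of the questionnaire outcomes in two sentences. The first gives the method: "Two-sample t tests and mixed-effect linear regression models will be used to assess the mean between-group differences". The second gives the adjustment: "Covariates such as age, education, socio-economic status (SES), stress and depression will be adjusted in the multivariable regression model". Neither sentence defines the groups, and neither says how or when stress and depression are measured.

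Section 3.3 (Psychosocial Questionnaires) describes what is collected: "validated measures of parenting confidence, relationship quality, infant bonding, and father involvement will be assessed". The schedule by time point is:

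- Baseline: "At baseline, each parent will complete the Revised Dyadic Adjustment Scale (RDAS) and the Postpartum Bonding Questionnaire (PBQ").
- Day before discharge (T-1): the RDAS, "the PBQ, and the Parenting Sense of Competence Scale (PSOC").
- After discharge: "At T+14 and T+30, each parent will complete the RDAS, the PBQ, the PSOC, and a Father Involvement Questionnaire".

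Parental stress appears elsewhere as an outcome. Section 2.2.1 uses parental HR and HRV "as indicators of physiologic stress in NICU parents during and after periods of KC". Section 1 says of fathers in the NICU: "These feelings and experiences may further translate into individual and interpersonal stress, anxiety, and diminished parenting confidence". It then suggests that father care may support them through this.

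**The concern.** A prespecified covariate needs a source and a time. Depression has neither here, and stress has no named measure. If the gap is filled at the analysis stage, someone chooses the covariates and their timing after the data are in hand.

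For stress, the measures most readily available are the trial's own outcome measures, mostly recorded during or after KC. Section 1 presents stress as part of what father care may relieve, and parenting confidence, measured by the PSOC, is a questionnaire outcome. A stress value taken after KC begins could therefore lie between the intervention and the outcome. Adjusting for it would change what the group coefficient means. At stake is the interpretation of the secondary results on confidence, relationship quality, bonding and involvement.

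**Working it through.** The plan gives no figure for this model. The power statement in section 5.1 (greater than 99%) is general and comes without a sample size, effect size or SD, so it cannot be reproduced and plays no part here. The check is a comparison of the listed covariates with the described data.

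**1. Is there a source?**

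| Covariate | Described source | When | Also an outcome? |
|---|---|---|---|
| Depression | none | – | no |
| Stress, by questionnaire | none named; the content of the saliva questionnaire is not given | T1, T2, T3 of each session | not stated |
| Stress, by saliva | cortisol (both parents), testosterone (fathers) | T1 just before KC, T2 30 minutes in, T3 30 minutes after | yes, secondary (2.2.2) |
| Stress, by sensor | parental HR and HRV | 1 hour before, 2 hours during, 1 hour after KC | yes, primary (2.2.1) |

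**2. Is the value taken before KC?** Two of the three saliva samples, and three of the four sensor hours (2 + 1 of 4), come after the session starts. T1 and the first sensor hour precede that parent's own session. However, they are taken from the parent doing that session, and the two sessions are planned for separate days. So in each family one parent of two has a T1 value before any study KC. The other parent's T1 follows the family's first session.

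**3. Why timing matters.** Take a generic two-group contrast G, post-KC stress S and score Y, with Y = cG + bS + error and S = aG + (baseline stress) + error. The total effect is c + ab. Adjusting for S leaves c = (1 − m) × total, where m = ab / total is the share running through stress. Adjusting for stress measured beforehand leaves c + ab in expectation.

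Illustration, with every input assumed (total effect 0.5 SD, slope b = −0.5):

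- m = 25%: 0.75 × 0.5 = 0.375 (simulation of 400,000 records: 0.373)
- m = 50%: 0.50 × 0.5 = 0.25 (simulation: 0.247)
- adjusted for baseline stress instead: 0.498 in both simulations

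This shows only that timing decides whether the adjustment is harmless. It does not estimate anything for this trial, because neither m nor the contrast G is given.

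**4. What is the contrast?** Section 3.3 gives every family one mother session and one father session and randomizes only the order. By T-1 both parents should have had their session, whichever order they were assigned. The groups in 2.2.2 can be the two orders or mothers versus fathers. No group goes without KC.

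**5. Which baseline scores exist?** Under the section 3.3 schedule, RDAS and PBQ are collected at baseline. PSOC first appears at T-1 and the father involvement questionnaire only after discharge. Section 2.2.2 can be read as placing all four at baseline; the detailed schedule does not.

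**The case against.** The strongest reply has five parts.

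- **The list is open.** It is introduced as a set of examples, so a model without stress and depression can be fitted, and the t tests need no covariates. A reader might infer that the analysis cannot be run at all. The documents do not support that. The gap is firm for depression as a listed covariate. For stress it is less firm, since biomarkers exist and the saliva questionnaire might hold a stress item.
- **Adjustment for a pre-KC value is ordinary practice, and 2.2.2 does not rule it out.** This stands. The plan may intend it, but it does not say so, and T1 is a pre-KC value for only one parent per family.
- **No KC-versus-none effect is estimated.** A reader might infer that the model removes a share m of the KC effect and is biased toward no effect. That does not follow, because the contrast is order or parent. Mother versus father is not randomized, and section 1 reports distress in both parents with different challenges for fathers. Pre-KC stress and depression could then be sensible covariates.
- **Physiologic stress around a session need not be the stress meant in 2.2.2.** True, but the covariate is undefined, and physiologic measures are the only described source.
- **Age, education and SES have no described collection form either.** Also true, so absence from the schedule does not prove that an item is uncollected. But these are not things a KC session is expected to change, so no problem of timing arises for them.

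**Conclusion.** The point holds as a gap in specification that should be closed. Stress and depression are named as covariates with no scheduled scale and no time point. Depression has no described data source. Stress is described only through measures that are themselves outcomes, and using values taken after KC begins could adjust for something KC is meant to change.

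No size can be attached. The attenuation formula needs a mediated share and a defined contrast, and the documents supply neither, so bias is a possibility and not a demonstrated result. The conclusion rests on reading section 3.3 as the full questionnaire schedule. An undescribed stress item in the saliva questionnaire would soften the point about source for stress, but not the point about timing. Only the secondary questionnaire outcomes are affected.

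**What to change.** Amend section 2.2.2 as follows.

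1. Remove stress and depression from the main adjustment set, or allow them only as values measured before the family's first KC session, with the instrument named. The same cut-off should apply to both parents, so T1 of the second session does not qualify.
2. Keep age, education and SES, and name where they are recorded.
3. Add the baseline score of the same scale as a covariate for RDAS and PBQ, and state that baseline precedes the first KC session. These scores are already collected, and using them should improve precision. It is not possible for PSOC or father involvement under the section 3.3 schedule; align the time points in 2.2.2 with that schedule.
4. State which groups the model compares: the randomized orders, or mothers versus fathers.

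Cost: wording only if stress and depression are dropped. Keeping depression requires a baseline instrument to be added to the schedule, which is a change in data collection. Keeping stress as a value before the first session for both parents would likewise need a measure that the schedule does not now describe.
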